IGF-1 and IGFBP-3			X				X								X	X	X
Gonadal hormone ^z			X				X								X	X	X
Exploratory storage samples (RNA, serum, and plasma)			X			X	X								X		
Pharmacogenetic (DNA) collection							X										
PK sample ^{aa}			X	X	X	X	X									X	

Abbreviations: Ab = antibody; ACPA = anti-citrullinated protein antibodies; CHQ-PF50 = Child Health Questionnaire-Parent Form 50;

DNA = deoxyribonucleic acid; DBW = double-blind withdrawal; ECG = electrocardiogram; eCOA = electronic Clinical Outcome Assessment;

eGFR = estimated glomerular filtration rate; EQ-5D-Y = European Quality of Life-5 Dimensions-Youth version; ERA = enthesitis-related juvenile idiopathic arthritis; ESR = erythrocyte sedimentation rate; ETV = early termination visit; hBcAb = hepatitis B core antibody; hBsAb = hepatitis B surface antibody;

hBsAg = hepatitis B surface antigen; HBV = hepatitis B virus; = hepatitis C virus; HIV = human immunodeficiency virus; HLA-B27 = human leukocyte antigen-B27; hsCRP = high-sensitivity C-reactive protein; ICF = informed consent form; IgA = immunoglobulin A; IgG = immunoglobulin G;

IgM = immunoglobulin M; IGF-1 = insulin-like growth factor-1; IGFBP-3 = insulin-like growth factor-binding protein-3; ILAR = International League of

Associations for Rheumatology; IWRS = interactive web-response system; JIA = juvenile idiopathic arthritis; JPsA = juvenile psoriatic arthritis; NK = natural killer; OLLI = open-label lead-in; PASI = Psoriasis Area and Severity Index; PedACR30 = Pediatric American College of Rheumatology 30 criteria; PK = pharmacokinetic(s); PPD = purified protein derivative; RF = rheumatoid factor; RNA = ribonucleic acid; SPARCC = Spondyloarthritis Research Consortium of Canada; TB = tuberculosis; tDaP = tetanus, diphtheria, and pertussis ; TIBC = total iron-binding capacity; TSH = thyroid-stimulating hormone; V = visit; W = week.

- a The OLLI period ends on the same day the DBW period begins.
- b Pharmacokinetic samples will be collected as described in Sections 9.5.2 and 9.5.3. Other baseline laboratory samples should be taken **before** administration of investigational product. Visit 5 (Day 1) will be used as the baseline for OLLI population. Safety/PK cohort will join the OLLI period at Visit 6. The actual study week and study day for the Safety/PK cohort are two weeks longer than that shown due to the additional 2-week safety/PK lead-in assessment period described in [Table JAHV.1](#).

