5.1.1. Screening and Baseline Periods

The duration of the Screening Period is up to 42 days prior to baseline. At screening, the parent or legal guardian will sign the informed consent form (ICF) and the patient will sign the assent form (as applicable) per local requirements prior to any study assessments, examinations, or procedures being performed ([Appendix 3](#)). All screening procedures will be performed according to the Schedule of Activities (Section 2).

Patients who receive a purified protein derivative (PPD) skin test at screening will need to return within 48 to 72 hours later to read the skin test. Treatments with concomitant JIA therapies during the study is permitted only as described in Section 7.7. Patients will remain on background cDMARDs, oral corticosteroid, NSAIDs, and/or analgesics if patients are on stable doses of these treatments at screening (Sections 6.2 and 7.7). Patients who have previously been treated with bDMARDs are eligible for the study. However, treatment must have been discontinued 4 weeks prior to screening for TNF inhibitors, IL-1 inhibitors, IL-6 inhibitors, or abatacept and 6 months prior to baseline for rituximab.

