Investigators should review the vaccination status of their patients and ensure that patients are up to date with all immunizations, and following the local requirements for vaccination guidelines and schedule for immunosuppressed patients. If a patient received a live vaccine within 28 days prior to baseline or intends to receive a live vaccine (except booster immunization with attenuated vaccine for measles, mumps, and rubella [MMR] or varicella zoster virus [VZV]) during the course of the study or up to 28 days after the last dose of investigational product, the patient is not eligible for the study. Considering the European League Against Rheumatism (EULAR) recommendations (Heijstek et al. 2011) and accumulated evidence (Groot et al. 2015; Sousa et al. 2017), booster vaccination for MMR or VZV may be considered if it is essential based on the local guideline and/or in the opinion of the investigator. If patients become eligible for vaccination with tetanus, diphtheria, and pertussis (tDaP) and/or pneumococcal conjugate vaccine during the study period according to local recommended schedule of vaccination, antibody titres to the vaccine will be evaluated pre-immunization and at 4 and 12 weeks post-immunization. A primary immune response will be assessed in patients who have never received tDaP or pneumococcal conjugate vaccines previously, and secondary/booster responses will be assessed if the patients have previously received the vaccines.

Patients who meet all of the inclusion and none of the exclusion criteria (Section 6) will continue to baseline.

At baseline, study eligibility for each patient will be reviewed, based on all inclusion and exclusion criteria (Section 6), and laboratory test results. Patients who meet all criteria will proceed to the subsequent period. Laboratory samples will be collected at baseline and all assessments should be completed before the patient takes the first dose of investigational product. Due to blood volume restrictions, some laboratory tests may not be collected. Laboratory samples are recommended to be collected as described in a sponsor-provided weight-based prioritization chart.

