5.1.3. Open-Label Lead-In Period

In the OLLI period, patients will receive oral baricitinib at a fixed dose by age group daily for approximately 12 weeks from baseline. This study uses “dual assessor” approach to avoid potential unblinding, which includes the Joint Assessor and the Physician Assessor (see Section 9). Each assessment should be evaluated by the same assessor at all study visits including unscheduled and the scheduled final study visit whenever possible.

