[20] Have had household contact with a person with active tuberculosis (TB) and did not receive appropriate and documented prophylaxis for TB.

[21] Have evidence of active TB or latent TB

a. Have evidence of active TB, defined in this study as the following:

- Positive PPD test (≥ 5 mm induration between approximately 2 and 3 days after application, regardless of vaccination history), medical history, and clinical features.
- QuantiFERON®-TB Gold test or T-SPOT®.TB test (as available and if compliant with local TB guidelines) may be used instead of the PPD test. Patients are excluded from the study if the test is not negative and there is clinical evidence of active TB.

Exception: Patients with a history of active TB who have documented evidence of appropriate treatment, have no history of re-exposure since their treatment was completed, have no clinical features of active TB, and have had a screening chest x-ray within the prior 6 months with no evidence of active TB may be enrolled if other entry criteria are met. Such patients would not be required to undergo the protocol-specific TB testing for PPD, QuantiFERON®-TB Gold test, or T-SPOT®.TB test, but must have had a screening chest x-ray within the prior 6 months.

b. Have evidence of untreated/inadequately or inappropriately treated latent TB, defined in this study as the following:

- Positive PPD test, no clinical features consistent with active TB, and a chest x-ray with no evidence of active TB at screening; or
- If the PPD test is positive and the patient has no medical history or chest x-ray findings consistent with active TB, the patient may have a QuantiFERON®-TB Gold test or T-SPOT®.TB test (as available and if compliant with local TB guidelines). If the test results are not negative, the patient will be considered to have latent TB (for purposes of this study); or
- QuantiFERON®-TB Gold test or T-SPOT®.TB test (as available and if compliant with local TB guidelines) may be used instead of the PPD test. If the test results are positive, the patient will be considered to have latent TB. If the test is not negative, the test may be repeated once within approximately 2 weeks of the initial value. If the repeat test results are again not negative, the patient will be considered to have latent TB (for purposes of this study).

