Exception: Patients who have evidence of latent TB may be enrolled if they complete at least 4 weeks of appropriate treatment prior to randomization and agree to complete the remainder of treatment while in the study.

Exception: Patients with a history of latent TB who have documented evidence of appropriate treatment, have no history of re-exposure since their treatment was completed, have no clinical features of active TB, and have had a screening chest x-ray within the prior 6 months with no evidence of active TB may be enrolled if other entry criteria are met. Such patients would not be required to undergo the protocol-specific TB testing for PPD, QuantiFERON®-TB Gold test, or T-SPOT®.TB test, but must have had a screening chest x-ray within the prior 6 months.

- [22] Major surgery within 8 weeks prior to screening or requiring major surgery during the study that in the opinion of the investigator in consultation with Lilly or its designee would pose an unacceptable risk to the patient.
- [23] History or presence of cardiovascular, respiratory, hepatic, gastrointestinal, endocrine, hematological, neurological, or neuropsychiatric disorders or any other serious and/or unstable illness that, in the opinion of the investigator, could constitute an unacceptable risk when taking investigational product or interfere with the interpretation of data.
- [24] History of a VTE or are considered at high risk of VTE as deemed by the investigator.
- [25] Largely or wholly incapacitated, such as being bedridden.
- [26] History of lymphoproliferative disease; or have signs or symptoms suggestive of possible lymphoproliferative disease, including lymphadenopathy or splenomegaly; or have primary or recurrent malignant disease.
- [27] History of chronic alcohol abuse, IV drug abuse, or other illicit drug abuse within the 2 years prior to screening.
- [28] Presence of significant uncontrolled neuropsychiatric disorder, history of a suicide attempt or suicidal ideation, or clinically judged by the investigator to be at risk for suicide.
- [29] History of hypogammaglobulinemia.
- [30] Body temperature $\geq 38^{\circ}\text{C}$ (100.5°F) at baseline.
- [51] Have experienced hypersensitivity to the active substance or to any of the excipients.

Prior/Concomitant Therapy

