6.3. Screen Failures

Individuals who do not meet the criteria for participation in this study (screen failure) may be rescreened up to 2 times. The interval between rescreenings should be at least 4 weeks from the previous screening date. Each time rescreening is performed the legal representative must sign a new ICF and the child would sign an assent, as applicable. The individual will be assigned a new identification number.

7. Treatments

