7.2. Method of Treatment Assignment

Patients who enter the PK lead-in period will be assigned a dose based on age. Pharmacokinetic samples will be collected as described in Section 9.5. Doses of subsequent patients who enter the PK lead-in period may be adjusted until a dose is found that produces exposures within the range produced by baricitinib 4-mg in adults with RA. All patients who enter the OLLI period will receive a fixed age-based dose of baricitinib as determined in the PK lead-in period.

Patients who meet the PedACR30 response criteria at the end of the OLLI period will be randomized in a 1:1 ratio (baricitinib age-based dose or matching placebo) to double-blind treatment at Week 12. The randomization will be stratified by history of prior bDMARD use (Yes versus No), the JIA category (polyarticular and extended oligoarticular versus ERA and

JPsA), and predose exposure ESR category (elevated [>20 mm/hour] and not elevated in the polyarticular JIA patients). Assignment to treatment groups will be determined by a computer-generated random sequence using an interactive web-response system (IWRS). The IWRS will be used to assign bottles containing double-blind investigational product to each patient. All patients <6 years of age will receive oral suspension. Patients ≥ 6 to <12 years old have the option of receiving the oral suspension. Patients >12 years will be supplied tablets only.

Site personnel will confirm that they have located the correct packages by entering a confirmation number found on the packages into the IVRS or IWRS before dispensing to the patient.

Refer to Section 5.1.2 for additional information regarding dosing in the Safety/PK assessment and OLLI period.

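### The latent-TB exception counts its 4 weeks of TB treatment back from randomization at Week 12, not from the first open-label dose of baricitinib

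*Protocol*

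**What the plan says.** Protocol 6.2, criterion [21]b, excludes children with latent TB that is untreated or not properly treated. The first exception beneath it lets such children in: they "may be enrolled if they complete at least 4 weeks of appropriate treatment prior to randomization and agree to complete the remainder of treatment". The rest of the TB course is then taken during the trial.

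Section 7.2 fixes when randomization happens. Children who meet PedACR30 at the end of the open-label lead-in "will be randomized in a 1:1 ratio (baricitinib age-based dose or matching placebo) to double-blind treatment at Week 12". Before that, under Section 5.1.3, "patients will receive oral baricitinib at a fixed dose by age group daily for approximately 12 weeks from baseline". The Safety/PK cohort has about 2 further weeks on drug first. Footnote b to Table JAHV.2 says: "The actual study week and study day for the Safety/PK cohort are two weeks longer than that shown".

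Eligibility is checked earlier. Section 5.1.1 says: "At baseline, study eligibility for each patient will be reviewed, based on all inclusion and exclusion criteria". Both schedules place the eligibility review only at Visit 1 and at baseline (Visit 2 in Table JAHV.1, Visit 5 in Table JAHV.2). Randomization is marked only at Visit 9.

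**The concern.** A rule that counts 4 weeks back from randomization protects a child only if dosing starts at randomization. Here every child takes baricitinib for about three months first, and nonresponders are never randomized at all. A site that follows the written time point could dose a child whose latent TB is still untreated and begin TB therapy weeks later without breaching the criterion.

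Section 6.2.1 says that criteria [12] to [21] exist to keep out children at raised risk of infection, and Section 9.2.2 names TB within an adverse event of special interest. What is at stake is the safety of a child with latent TB during JAK inhibition. The efficacy inference is not involved.

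**Working it through.** No sample-size, power or alpha figure bears on this point, so there is no stated result to reproduce. The check is a timeline.

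**Inputs**
- Required TB treatment: 4 weeks (28 days) before randomization (Protocol 6.2, [21]b exception).
- First dose to randomization: about 12 weeks for direct entry to the open-label lead-in (5.1.3, 7.2).
- First dose to randomization, Safety/PK cohort: 2 + 12 = about 14 weeks (5.1.2; Table JAHV.2, footnote b).
- Screening: "The duration of the Screening Period is up to 42 days prior to baseline" (5.1.1).
- PPD skin test: read at 48 to 72 hours, so up to 3 days (5.1.1).
- TB blood test that is not negative: "the test may be repeated once within approximately 2 weeks of the initial value" (6.2, [21]b), taken as 14 days.
- Planned numbers: 197 enter the lead-in and 128 are randomized, at an assumed 65% PedACR30 response (10.1).

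**Latest start of TB treatment under the literal rule**

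Weeks on drug = weeks from first dose to randomization − 4.
- Direct entry: 12 − 4 = about 8 weeks.
- Safety/PK cohort: 14 − 4 = about 10 weeks.

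**Whether the written deadline can be checked or reached**
- At baseline, a condition that may be met up to Week 12 cannot yet be verified. At Visit 9, no eligibility review is scheduled.
- Nonresponders never reach randomization. On the planned numbers that is 197 − 128 = 69 of 197 children, or 35%, who would take baricitinib in the lead-in with no TB-treatment deadline ever falling due. This counts all nonresponders. How many of them would have latent TB is unknown.

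**Whether another passage supplies a pre-dose deadline**

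None does. The TB footnotes to the two schedules (n in Table JAHV.1, p in Table JAHV.2) cover testing, chest x-ray and previously treated children only. Elsewhere the protocol does name a pre-dose time point when it wants one. Criteria [12], [15], [36] and [38] count back from baseline, and the pregnancy-test footnotes require a result before the first dose.

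**Whether 28 days of treatment fits in screening if the deadline moves to the first dose**

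Spare days = 42 − days to a TB result − 28.
- PPD route: 42 − 3 − 28 = 11 days.
- Repeated blood test: 42 − 14 − 28 = 0 days.

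The documents give no laboratory turnaround time. It is taken as 0 days here, and each day of turnaround removes one day from these margins.

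**The case against.** The best reply is that this is loose wording inside a check that takes place before dosing.

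- **Grammar.** The sentence separates something the child completes (the 4 weeks) from something the child agrees to do later (the remainder). That implies the 4 weeks are already done at enrollment, and Appendix 1 defines enrolling as assignment to a treatment.
- **Timing of review.** Section 6.2 applies the exclusions at screening and/or baseline, and the only scheduled reviews are there. On the literal reading the rule could never be verified. A child with untreated latent TB at baseline meets [21]b and has not yet earned the exception.
- **Backstops.** Criterion [12] lets the investigator exclude a child whose infection poses an unacceptable risk. Section 8.1.3 provides for stopping study treatment in a child enrolled against the criteria.
- **Remoteness.** The 8 and 10 weeks require a site to find latent TB, dose anyway and hold back TB treatment for about two months. Nothing suggests that this happened.

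Much of this stands as evidence of intent: a pre-dose deadline was probably meant, and a careful site may well apply one. It does not change the time point written, and the protocol places randomization at Week 12. The lack of any review at Visit 9 also shows that the rule does not work as written. The backstops are weak. Criterion [12] is discretionary, and Section 8.1.3 applies only if the criterion was breached, which on the literal wording it was not. The 8 and 10 weeks are indeed worst-case limits.

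**Conclusion.** The concern holds, and it is minor. The deadline in the latent-TB exception is tied to the wrong event for a design with an open-label lead-in. Taken literally, it allows TB treatment to begin up to about 8 weeks after the first dose of baricitinib, or about 10 weeks in the Safety/PK cohort. These limits assume nominal visit timing and a site that reads the criterion at its word.

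A child with 4 weeks of treatment already completed at baseline satisfies the rule on either reading and is not affected. The documents give neither a latent-TB frequency nor a reactivation risk over this interval, so no expected number of affected children or events can be given. Power, alpha and the primary analysis do not change.

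**What to change.** In the exception under [21]b, replace the reference to randomization with the first dose of investigational product (Visit 2 for the Safety/PK cohort, Visit 5 for all others). Keep the rest of the sentence, including the commitment to finish TB treatment during the study. Permitted baricitinib exposure before the 4 weeks are complete then falls from about 12 weeks (about 14 in the Safety/PK cohort) to none, and the condition can be verified at the baseline review already scheduled.

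The change is one phrase, though in an eligibility criterion it needs a protocol amendment, which goes to the ethical review boards (Appendix 3.1.3). Appendix 7 shows that it would still have had effect under amendment (d): the lead-in was enrolling ages 9 to <18, and the Safety/PK cohort for ages 2 to <6 had yet to start.

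The downside is a later start or a rescreen for a few children, mainly those whose blood test was repeated and who have no spare days. Section 6.3 already allows up to two rescreenings: "The interval between rescreenings should be at least 4 weeks from the previous screening date".

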6.2.1. Rationale for Exclusion of Certain Study Candidates

The rationale for the exclusion criteria is as follows:

- Exclusion Criteria [7] to [11] exclude individuals with conditions that may confound safety or efficacy analyses.
- Exclusion Criteria [12] to [21] exclude individuals who are at an increased risk for infections or infectious complications.
- Exclusion Criteria [22] to [30], and [51] exclude individuals with previous or concomitant medical conditions that increase the risk for their participation in the study.
- Exclusion Criteria [31] to [41] exclude individuals who are taking or who may take JIA medications or treatments that interfere with the ability to assess the safety and efficacy of baricitinib.
- Exclusion Criteria [42] to [43] exclude individuals with laboratory parameters that may increase the risk for their participation in the study.
- Exclusion Criteria [44] to [50] exclude individuals whose participation in the study may introduce bias.

6.3. Screen Failures

Individuals who do not meet the criteria for participation in this study (screen failure) may be rescreened up to 2 times. The interval between rescreenings should be at least 4 weeks from the previous screening date. Each time rescreening is performed the legal representative must sign a new ICF and the child would sign an assent, as applicable. The individual will be assigned a new identification number.

7. Treatments

7.1. Treatments Administered

This study involves a comparison of baricitinib dose, by age (4-mg for children ≥ 9 years of age and adolescents 12 to < 18 years of age and 2-mg for children < 9 years of age as the starting dose; see Appendix 7 for updated dosing based on the current data), with placebo in the DBW period. The dosages will be adjusted if the interim analyses after the Safety/PK period demonstrate that the profiles are not comparable with the target PK or safety profiles in adults. Therefore, a 1-mg dose is described in [Table JAHV.5](#) should this be needed.

Baricitinib will be dosed as tablets or oral suspension QD based on the age of the patient at Visit 2 (for patients enrolled in the Safety/PK portion) and at Visit 5 (for all other patients); formulation will not change during the study. Baricitinib should be taken with sufficient water or fluid to allow easy swallowing of the medication. All patients < 6 years of age will receive oral suspension. Patients ≥ 6 to < 12 years old have the option of receiving the oral suspension. Patients > 12 years old will be supplied tablets. Based on PBPK modeling, initial doses will be 4-mg for adolescents 12 to < 18 years old and in children ≥ 9 to < 12 years old, and 2-mg in children < 9 years old to produce exposures similar to those in adults after 4-mg QD administration. Refer to Section 5.5 for additional information. [Table JAHV.5](#) shows the treatment regimens.

Table JAHV.5. Treatment Regimens

Treatment Group	Treatments Administered	
	Safety/PK and OLLI Period	DBW Period
Baricitinib 4-mg	Baricitinib 4-mg oral QD tablet Baricitinib 2-mg/mL oral suspension	Baricitinib 4-mg oral QD tablet Baricitinib 2-mg/mL oral suspension
Baricitinib 2-mg	Baricitinib 2-mg oral QD tablet Baricitinib 2-mg/mL oral suspension	Baricitinib 2-mg oral QD tablet Baricitinib 2-mg/mL oral suspension
Baricitinib 1-mg	Baricitinib 1-mg oral QD tablet Baricitinib 2-mg/mL oral suspension	Baricitinib 1-mg oral QD tablet Baricitinib 2-mg/mL oral suspension
Placebo comparator	N/A	Baricitinib 4-mg placebo oral QD tablet Baricitinib 2-mg placebo oral QD tablet Baricitinib 1-mg placebo oral QD tablet Baricitinib 2-mg/mL placebo oral suspension

Abbreviations: DBW = double-blind withdrawal; eGFR = estimated glomerular filtration rate; N/A = not applicable; OLLI = open-label lead-in; PK = pharmacokinetics; QD = once daily.

Note: Initial doses of baricitinib 4-mg for adolescent patients (12 to < 18 years of age) and children ≥ 9 years of age and baricitinib 2-mg for children < 9 years of age will be given. The oral suspension dose may be administered as 4-mg, 2-mg, 1-mg, and 0.5-mg as needed.

Note: Patients with renal impairment or renal immaturity (defined as eGFR < 60 mL/min/1.73 m²) at baseline will have their dose reduced by 50%. Patients receiving the 1-mg dose who have renal impairment or renal immaturity will receive a dose-of 0.5-mg using the oral suspension.

The investigator or appointed designee is responsible for the following:

- Explaining the correct use of the investigational agent(s) to the parent or legal guardian
- Verifying that instructions are followed properly
- Maintaining accurate records of investigational product dispensing and collection
- At the end of the study returning all unused medication to Lilly, or its designee, unless the sponsor and sites have agreed that all unused medication is to be destroyed by the site, as allowed by local law.

Placebo tablets are composed of lactose monohydrate, microcrystalline cellulose, croscarmellose sodium, and magnesium stearate. Tablet coating is comprised of polyvinyl alcohol—partially hydrolyzed, titanium dioxide, polyethylene glycol 3350, talc, lecithin (soya), and iron oxide red.

